Each participant will be enrolled in the study from the time of enrollment during or shortly following hospitalization or cath lab encounter to 12 weeks post-randomization after discharge. Study visits will occur at baseline (at patient bedside or via follow up call) and 12 weeks post-randomization post-discharge (at Bayview Clinical Research Unit, up to maximum 18 weeks post- (to account for delays related to clearance of procedure-related precautions (e.g. sternal precautions following CABG surgery) or insurance approval for starting in-person CR sessions), whichever occurs earlier). Patients in the intervention arm will also be encouraged to have a lipid panel rechecked (ordered by the primary team at discharge) at their local laboratory 4 weeks post-discharge. Patients in the control group will receive reminders from the study team to participate in the final study visit.

Date: 10.09.2024

Principal Investigator: [name], MHS

Application Number: IRB00308410

Blinding

Although blinding participants or study team members enrolling patients is not possible, outcome assessors will be blinded to intervention allocation. We will instruct study participants not to discuss allocation with study personnel prior to both the initial and follow-up assessments.

Definition of treatment failure or participant removal criteria

For participants in the intervention group: If the participant stops using the Corrie DHI for >30 days or does not respond to phone calls after failing to complete the study surveys after 7 days, the participant will be considered lost to follow up.

For participants in the Control group: If the participant does not respond to phone calls after failing to complete the study surveys after 7 days, the participant will be considered lost to follow up.

Description of what happens to participants receiving therapy when study ends or if a participant's participation in the study ends prematurely

When the study ends or a participant's participation in the study ends prematurely, participants in the intervention group may keep their app (in which case their use will continue to be tracked). Any other devices that were provided during the study will be expected to be returned.

Participants may be given the option to participate in future research studies.

5. Inclusion/Exclusion Criteria

Inclusion Criteria

- Adult aged 18 years or older
- Individuals presenting to the hospital for the following conditions or interventions: Acute myocardial infarction (STEMI or NSTEMI type 1), Coronary artery bypass grafting (CABG), coronary artery angioplasty/stenting (PCI), heart valve surgery, transcatheter aortic valve replacement (TAVR).

Exclusion Criteria

- Does not speak English
- Physical disability that would preclude safe and adequate exercise performance
- High risk for falls (Score >13 on Johns Hopkins Fall Risk Assessment Tool – see Supplemental documents)
- Visual or hearing impairment which precludes the use of the intervention
- Mental or behavioral impairment leading to inability to cooperate with study procedures
- Clinically significant depression (uncontrolled) or history of psychosis
- Pregnancy
- Left ventricular ejection fraction <40%

Date: 10.09.2024

Principal Investigator: [name], MHS

Application Number: IRB00308410

- Unaddressed severe valvular heart disease (e.g. severe: aortic stenosis, aortic regurgitation, mitral stenosis, mitral regurgitation)
- Hypertrophic obstructive cardiomyopathy with peak resting left ventricular outflow gradient of >25 mmHg
- Atrial fibrillation with uncontrolled ventricular rate (Heart rate >110 at rest) at baseline assessment
- Untreated high degree atrioventricular block (ie. Mobitz II or complete heart block without permanent pacemaker)
- History of cardiac arrest or sudden death
- Presence of cardiac defibrillator
- Uncontrolled resting arterial hypertension (Systolic blood pressure >200 mmHg or diastolic BP >110mmHg) at baseline assessment
- Unrepaired aortic dissection
- Incomplete/failed coronary revascularization procedure of culprit artery
- Significant complications from myocardial infarction, cardiac surgery, or cardiac procedure including: congestive heart failure (LVEF <40%), cardiogenic shock, signs/symptoms of persistent post-procedure ischemia, and unaddressed post-procedural arrhythmia or conduction complications (e.g. new left bundle branch block post-TAVR without pacemaker)

If an eligible patient is deemed clinically unstable and unable to participate at the time of initial assessment, the research team member may return at a later date for reassessment.

6. Drugs/ Substances/ Devices

1. The Corrie app is available on both iPhone and Android platforms. In discussion with an FDA-consultant, because the functionality of the app is as an organizational and navigational tool for patients, it does not require pre-approval from the FDA before use with patients. It falls within the category of mobile apps for which the FDA is exercising enforcement discretion.
2. The Apple Watch, Fitbit, and Omron blood pressure cuff all have received FDA clearance and are safe for patient use (see supplementary documents).

7. Statistical Analysis

The primary outcome measure of the study is the difference in distance participants walked (i.e. functional capacity) between the intervention and usual care groups, as measured by the 6MWT at final study follow-up at 12 weeks post-randomization. Based on the estimates from a prior RCT ⁴¹ in patients with acute coronary syndrome in a smartphone-based, cardiac rehabilitation program, but also accounting for a significant anticipated proportion of cardiac surgery and TAVR patients in our trial population, we assume a pooled standard deviation of 107 meters for follow-up 6MWT distance. and a minimally clinically important difference of 30 meters in 6MWT distance.⁴²

Date: 10.09.2024

Principal Investigator: [name], MHS

Application Number: IRB00308410

For the trial to demonstrate noninferiority with 80% power, assuming a pooled standard deviation of 107 meters for the follow-up 6MWT and a true 6MWT difference in favor of the Corrie HCR program of 30 m, 160 patients will be required (80 per group) to exclude a difference of >12.5 m in favor of the usual care group. The noninferiority margin of 12.5 m was chosen to represent about 40% of the minimum important difference of 30 m in 6MWT as identified in previous studies. Accounting for an attrition rate of 20% during follow-up after randomization, a total of 200 (100 per group) participants will be randomized in a 1:1 ratio to the 2 treatment arms. In order to accrue 200 patients for randomization, we expect to recruit up to 300 patients, until target randomization number has been met. We will compare the mean level of 6MWT at 12 weeks post-randomization between the intervention and control groups using a generalized linear regression model. The sample size calculation was performed using the TWOSAMPLEMEANS statement in SAS version 9.4 procedure PROC POWER (SAS Institute Inc., Cary, NC), in which the null value option was specified to represent the noninferiority margin.

If a participant has an adverse event that results in them being discontinued from the study or does not engage with the intervention, that participant will be included in the intention-to-treat analysis, which is the primary form of analysis for our study.

In addition to the primary intention-to-treat analysis, a pre-specified, per-protocol analysis will be conducted 1) inclusive of intervention group participants who remain active in the study and engage with the intervention, and separately 2) among those participants (in both control and intervention arms) who have completed at least two in-person CR sessions, in order to assess the efficacy of the intervention.

In addition, pre-specified subgroup analyses will be performed, stratified by: age, sex, treatment modality (cardiac surgery, catheter-based intervention, or medical therapy), and LDL-C level (threshold LDL-C \geq 55mg/dL).

8. Risks

Risks include adverse events during off site/CR exercise. To minimize this risk, we have the following measures in place: (1) We will only enroll participants in the study who do not have high risk clinical characteristics for exercise based on AACVPR criteria. (2) We will ask patients to refrain from unmonitored exercise until they undergo further assessment for high risk exercise features during two in-person CR sessions and are determined to be low to moderate risk for exercise. If individuals are deemed high risk, they will be encouraged to continue attending in-person CR sessions for safe, monitored exercise, and will be advised to perform lower levels of usual physical activity (e.g., walking and range of motion exercises) as advised by the CR staff. (3) We will provide weekly check-ins with patients to guide them accordingly if their vitals are not within normal range or report concerning symptoms. The guide for these check-ins has been compiled based on the Johns Hopkins in-person CR protocols and is attached in supplementary document section. (4) Dashboard will

Date: 10.09.2024

Principal Investigator: [name], MHS

Application Number: IRB00308410

be monitored once a day (during business hours). Any symptoms or red flag vitals will be managed as per standardized operating procedure.

The 6MWT is a low-risk medical test that is performed under supervision of a trained exercise physiologist. Potential risks include chest pain, shortness of breath, leg cramps, losing balance, excessive sweating, and falling.

Another risk is breach of confidentiality. The Corrie Health digital platform uses a high level of personal security password protection and encryption to meet privacy standards. The study team will disclose to the participant and IRB if a breach of confidentiality occurs.

Financial risk is minimized by covering costs for transportation and parking for in-person visits for the intervention group using study research funds.

9. Benefits

Participants in the intervention group will be given access to the Corrie DHI. Through this intervention they may benefit from greater knowledge about their diagnosis, risk factors, how to modify their risk factors and develop self-efficacy to continue risk factor modification after completion of the program. Furthermore, they may benefit from off-site/home based physical activity (after it is determined to be safe by in-person CR assessment) and develop skills that help them manage their medications as well as follow-up appointments with their primary care provider, cardiologist, and in-person CR. Patients enrolled in usual care may not derive significant direct benefit, aside from knowledge gained during the consent process and health information gained through measurements taken at the final study visit. Moreover, the data that they contribute as a research participant could help others in the future.

10. Payment and Remuneration

For participants in the intervention arm, the Corrie App, Smartphone and/or smartwatch, Blood pressure monitor, and exercise resistance bands will be provided to participants (if they do not own one) at no cost to them. If a participant stops engaging with the intervention for at least 1 week during the study or within 6 months of study completion, we will ask devices to be returned to study team so that they can be recycled for use for other participants or future studies. All participants will be compensated via \$50 e-gift cards at the completion of the study, after the final study visit, for which transportation and parking fees will be covered by the study research funds. For the intervention arm, transportation and parking costs associated with the two in-person CR visits will also be covered by the study research funds.

11. Costs

Date: 10.09.2024

Principal Investigator: [name], MHS

Application Number: IRB00308410

Costs associated with smartphone and smartwatch application development, costs for iShare smartphone devices, blood pressure monitors, resistance bands and \$50 gift cards have been paid through American Heart Association's Strategically Focused Research Network Grant (Grant number 134503). Apple Watches for iShare program have been provided by Apple Inc.

12. Johns Hopkins Serving as a Coordinating Center

Johns Hopkins Medicine is serving as the single IRB for this study. It is the preference of Johns Hopkins Medicine IRB to use the SMART IRB reliance agreement as the basis of reliance. The SMART IRB master reliance agreement was created in 2016 to harmonize and streamline the IRB review process for multisite studies. It enables reliance on a study-by-study basis, clearly defines roles and responsibilities of relying institutions and reviewing IRBs, and eliminates the need to sign reliance agreements for each study [e.g., a non-SMART IRB agreement]. 900+ institutions have already signed onto this agreement and are actively using it as the basis of reliance for multisite projects. Sites that will rely on JHM IRB are still responsible for conducting a local context review prior to the start of research at their site and for following any local and institutionally required policies as it applies to research at their site [e.g., reporting of unanticipated problems].

The JHM PI has contact information for all sites, each participating center has an active FWA with OHR on file. Each site will collect and manage data as described in the protocol. Sites will notify the coordinating center of adverse event reports and deviations via the RF3 and RF4 forms. Sites will complete a continuing review enrollment form that will be submitted at the time the parent continuing review is submitted. As part of any site conference calls, the coordinating center will inform sites of coordinating centers prompt reporting policy and will ensure they are submitted to JHM IRB per requirements.

References:

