- As assessed by a Markov Model of cost-effectiveness³¹ – the hospital costs (in US dollars) for emergency department (ED) visits and hospital readmissions will be compared between the intervention and usual care groups.

For the intervention arm only, we will measure intervention user satisfaction and engagement:

- User Engagement – Total number of interactions in the smartphone app and interactions with specific features of the smartphone app per participant, collected via the Corrie Health Platform User Analytics
- User Satisfaction – System Usability Scale modified for Corrie³²

Table 1. Composite score components of secondary cardiovascular prevention metric
Cardiovascular Secondary Prevention Metric Components

Ideal	Diagnosis of diabetes: HbA1c <7% No diagnosis of diabetes: HbA1c <5.7%
-------	---

Date: 10.09.2024

Principal Investigator: [name], MHS

Application Number: IRB00308410

Intermediate	Diagnosis of diabetes: HbA1c 7-7.9% No diagnosis of diabetes: HbA1c 5.7-6.4%
Poor	Diagnosis of diabetes HbA1c \geq 8% No diagnosis of diabetes: HbA1c \geq 6.5%
Ideal	SBP <130 and DBP <80 mmHg
Intermediate	SBP 130-139 and DBP <90 or SBP <130 and DBP 80-89 mmHg
Poor	SBP \geq 140 or DBP \geq 90 mmHg
Ideal	LDL-C cholesterol <70 mg/dL
Intermediate	LDL-C cholesterol 70 - 99 mg/dL
Poor	LDL-C cholesterol \geq 100mg/dL
Ideal	BMI <25 kg/m ²
Intermediate	BMI 25-29 kg/m ²
Poor	BMI \geq 30 kg/m ²
Ideal	\geq 150 min/wk moderate or \geq 75 min/wk vigorous or \geq 150 min/wk moderate and vigorous physical activities
Intermediate	1-149 min/wk moderate or 1-74 min/wk vigorous or 1-149 min/wk moderate and vigorous physical activities
Poor	None
Ideal	Never smoker (<100 cigarettes in lifetime)
Intermediate	Former smoker
Poor	Current smoker
Ideal Diet	Rate Your Plate 64 - 81
Intermediate Diet	Rate Your Plate 46 - 63
Poor Diet	Rate Your Plate 27 - 45
For each component ideal profile is consistent with a score of 2, intermediate profile is consistent with a score of 1 and poor profile with a score of 0. Subsequently a total score ranging from zero (worst CV Health) to 14 points (best CV health) is calculated.	

3. Background

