the DHI (Table 2), which could promote digitally-enabled hybrid CR uptake at scale and reduce the gap in lifesaving CR access and utilization.

[name], MD, MHS, PI, has extensive clinical and research experience the CR space. She directs the Johns Hopkins Cardiac Rehabilitation Center.

Table 2. Components of DHI: The Corrie Hybrid Cardiac Rehabilitation Program

Patient Level - Corrie App, Smartwatch, Blood pressure monitor, exercise resistance bands, Corrie "Coach" (attached in supplemental documents) and contextual motivational messages (attached in supplemental documents)
Clinician Level – Reminder for CR referral, Reminder for ordering repeat lipid panel upon discharge (as recommended by professional society guidelines), In person assessment and two monitored and supervised sessions for personalization of home exercise, improving confidence and self-efficacy for home exercise, and assessment of safety of home exercise

Figure 1. Core components of Cardiac Rehabilitation/Secondary Prevention Programs as per American Heart Association and American Association of Cardiovascular and Pulmonary Rehabilitation Statement.³⁶

4. Study Procedures

General Overview:

We will conduct a multi-site, parallel arm randomized clinical trial to evaluate the efficacy of the intervention plus usual care compared to usual care alone (1:1 allocation ratio) in individuals who present to study hospitals with the following diagnosis or interventions: ST elevation myocardial infarction (STEMI), Type 1 non ST elevation myocardial infarction (NSTEMI), Atherosclerotic Cardiovascular Disease (ASCVD) requiring coronary revascularization via percutaneous coronary intervention (PCI) or coronary artery bypass graft surgery (CABG), and valvular heart disease interventions including valvular heart surgery and transcatheter aortic valve replacement (TAVR). We will evaluate the primary outcome and secondary outcomes at 12 weeks post-randomization. Study sites include Johns Hopkins Hospital, Johns Hopkins Bayview Medical Center, Howard County Hospital, and Suburban Hospital.

Enrollment, Randomization and Measurements:

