18. Individuals who are randomized to the intervention who do not own a smartphone or smartwatch will be provided with devices. This program, called iShare, was previously established and successfully implemented by our study team in the MiCORE trial.¹³ Participants will be allowed to keep the devices even after the study ends, if desired, to facilitate subsequent phases of CR and potential long-term studies in the future. If

patients decide to leave the program during the study or within 6 months of study completion, they will be expected to return the devices to the study team.

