27. All patients randomized to the intervention will receive weekly virtual check-ins consisting of a video call (unless patient opts out of the video component for only audio call) from a trained exercise physiologist health coach, starting within 1 week from randomization. These virtual check-ins will be used to guide patients with individualized risk factor modification, stress reduction and on adapting their exercise prescription (for those cleared for home exercise), where the latter will be performed by a study exercise physiologist. If during the virtual check-in the patient reports high risk symptoms (e.g. chest pain), the health coach will follow Cardiac Rehabilitation Standard Operating Procedure scenarios (attached in supplementary documents) to handle the different emergencies, and they will be asked to pause the exercise component of the intervention until safety of returning to exercise is determined by their caring clinician. The Corrie Dashboard will be monitored once a day and any red flags will be handled similarly as per the Standard Operating Procedure. Patients will be informed that the study team cannot replace their care teams and patients should contact their clinicians, call 911 or go to emergency room when experiencing severe symptoms or abnormal vital signs. Virtual, synchronous, audiovisual group-based education sessions will be offered weekly by the exercise physiologist health coach. These sessions will supplement the weekly virtual check-ins for patients randomized to the intervention. These educational, patient-support/social networking forums aim to enhance the social experience of this virtual model. Social media platforms (such as Facebook group), moderated by the study team, may be used to facilitate voluntary communication and interaction among study participants for community-building purposes.

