		Number of in-person and off – site (asynchronous) exercise sessions
		Surveys delivered via email through REDCap
		Adverse Outcome Questionnaire (myocardial infarction, stroke, Emergency room visit, hospitalization or death)
		For individuals randomized to intervention arm
		User Engagement - Total number of interactions in the smartphone app and feature specific interactions using the smartphone app per participant, collected via the Corrie Health Platform User Analytics
		User Satisfaction – System Usability Scale
		Cost Data
		The hospital costs (in US dollars) for emergency department (ED) visit, hospital readmission, and acute myocardial infarction (MI) will be compared between intervention and usual care groups.
*If these laboratory values are not available patient's care team will be reminded to place an order in EPIC as these values should be		*Bloodwork during the follow – up visit will be obtained during the study visit and costs will be charged from the study budget.

Date: 10.09.2024

Principal Investigator: [name], MHS

Application Number: IRB00308410

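### The cost-effectiveness outcome lists only hospital costs. Program costs borne in the intervention arm alone are missing, which favours the intervention, and rehabilitation session costs are missing in both arms.

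*Combined protocol and SAP*

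**What the plan says.** Section 2, under Cost of care, introduces the outcome with "As assessed by a Markov Model of cost-effectiveness" and then states what is compared: "the hospital costs (in US dollars) for emergency department (ED) visits and hospital readmissions will be compared between the intervention and usual care groups". The Cost Data row of Table 3 gives a slightly different list: "The hospital costs (in US dollars) for emergency department (ED) visit, hospital readmission, and acute myocardial infarction (MI) will be compared". Both are confined to hospital costs. Section 7 contains no cost analysis. No section states the model's perspective, time horizon, health states or unit of effect.

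The protocol gives several resources to the intervention arm only:

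- **Devices.** Table 2 lists "Corrie App, Smartwatch, Blood pressure monitor, exercise resistance bands". Section 4, item 18 adds: "Individuals who are randomized to the intervention who do not own a smartphone or smartwatch will be provided with devices". Section 10 likewise limits provision to items the participant does not own.
- **Onboarding.** Section 4, item 19 describes individual technology onboarding by a study team member.
- **Coaching.** Section 4, item 27: "All patients randomized to the intervention will receive weekly virtual check-ins consisting of a video call". The same item offers weekly group education sessions and has the dashboard checked once a day.
- **Travel.** Section 4, item 26 and Section 10 pay travel and parking for the two required CR sessions in this arm only.

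Section 11 says a research grant paid for phones, blood pressure monitors and bands, and that "Apple Watches for iShare program have been provided by Apple Inc".

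Center-based CR is encouraged in both arms (Section 4, item 26). The same item allows for intervention participants who stop after the first two sessions and exercise at home. Session counts are collected (Section 2; Table 3) but are not given a cost.

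**The concern.** A cost-effectiveness result sets the extra cost of a strategy against its extra effect. The extra cost must include the cost of delivering the strategy. Here the named costs are only those the program might reduce, and none of those it adds. On that list, any fall in emergency visits or readmissions would read as a saving, whatever the program costs to run. Costing from the study budget would not fully repair this, because the donated watches would enter at zero.

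The two cost lists also differ on acute MI. An MI admission is normally a readmission as well, so if the Table 3 categories were summed it could enter twice.

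What is at stake is any statement that the program is cost-effective or cost-saving. The outcome is neither primary nor key secondary, and no efficacy or safety conclusion depends on it.

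**Working it through.** The protocol states no cost figure, so there is nothing to reproduce. The check is an accounting identity followed by an illustration.

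**1. Identity.** Per participant, intervention minus usual care:

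true incremental cost = H + P + S

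- H = difference in hospital cost (the only term the plan lists)
- P = mean program cost in the intervention arm (devices averaged over the arm, onboarding, coaching, CR travel)
- S = difference in center-based CR session cost

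Reported minus true = H − (H + P + S) = −(P + S).

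**2. Sign of each part.** P is above zero at any prices, because coaching is given to everyone in that arm and to nobody in the other. Omitting P therefore always favours the intervention. S can have either sign: negative if home exercise displaces center sessions, positive if the program raises attendance. The total error favours the intervention unless displaced sessions × price per session exceeds P.

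**3. Illustrative size of P.** All prices are assumptions. Twelve check-ins follows from weekly contact over 12 weeks; two trips follows from the two required sessions.

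- Low: 50 (devices) + 12 × 20 + 2 × 10 = 50 + 240 + 20 = $310
- Middle: 300 + 12 × 40 + 2 × 25 = 300 + 480 + 50 = $830
- High: 1,000 + 12 × 75 + 2 × 50 = 1,000 + 900 + 100 = $2,000

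For the 100 participants planned per arm this is $31,000, $83,000 or $200,000. Onboarding, group sessions and dashboard review are not in these sums.

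**4. Could displaced CR sessions offset P?** Sessions displaced per participant needed = P ÷ price per session (assumed):

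| Price per session | P = $310 | P = $830 | P = $2,000 |
|---|---|---|---|
| $50 | 6.2 | 16.6 | 40.0 |
| $100 | 3.1 | 8.3 | 20.0 |
| $150 | 2.1 | 5.5 | 13.3 |

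Section 2 tracks completion of 2, 12, 24 and 36 sessions. A drop from 36 to 2 would displace 34, so every cell except 40.0 is arithmetically possible. The documents therefore do not fix the sign of P + S.

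**5. Devices.** The device part of P depends on how many participants already own devices and on reuse. Section 4, item 18 lets participants keep devices, while the end-of-study paragraph of Section 4 expects provided devices back and Section 10 foresees recycling after disengagement. These statements need reconciling before a device cost can be set.

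**The case against.** The best reply is that silence is not exclusion. Section 2 names a model and a comparison to be reported; it does not say these are the model's only inputs, and a Markov model needs much else that the protocol leaves unstated. On this view the fault is thin specification. That stands in part: perspective, horizon and unit of effect are indeed missing. But both places that define the outcome name only hospital costs, and nothing elsewhere brings program costs in. Followed as written, the list gives an incomplete incremental cost.

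A second reply is that the program may pay for itself by replacing center sessions. This also stands in part. A reader might infer that the whole cost result is biased toward the intervention. The documents do not support that, because session costs are unlisted as well and the offset is possible. Nor do they show that displacement will occur: Section 1 has the program complement usual care, attendance is encouraged in both arms, and higher attendance would add to the bias.

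A reader might also infer that MI admissions will be counted twice. Table 3 lists categories to compare and does not say they are summed, so this is a risk, not a finding.

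Finally, it is tempting to convert P into a number of readmissions that must be avoided to break even. The documents give no prices. Such a figure would also ignore savings on emergency visits and displaced sessions. Break-even is moreover a test of cost saving; cost-effectiveness allows a positive incremental cost.

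**Conclusion.** The point holds in a limited form. The stated cost list omits a program cost that is positive and falls only on the intervention arm, and that omission favours the intervention. A hospital saving smaller than the program cost could be reported as a saving when, before any difference in CR sessions, it is a net cost. The direction of the total error is not established, because CR session costs are missing too.

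The size cannot be computed from the documents. The range of $310 to $2,000 per intervention participant rests wholly on assumed prices and on about 12 coach contacts. Two qualifications apply. Devices go only to those who lack them, so their cost is an arm average. Travel to the final study visit is paid in both arms (Section 4, item 29), so only travel to the two required CR sessions belongs in the omission.

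The plan should be corrected before any cost-effectiveness claim is made.

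**What to change.** Use one cost list, identical in Section 2 and Table 3, that adds to the hospital costs:

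- **Devices**, averaged over the intervention arm, valued even when donated or grant-funded, and allowing for ownership and reuse.
- **Staff time** for coaching, group sessions, exercise prescription and dashboard review. The protocol does not say this time is recorded; if it is not, estimate it from the number of scheduled contacts.
- **Onboarding**, and **paid travel** to the two required CR sessions.
- **Center-based CR sessions in both arms**, using the session counts already collected. Adding program costs without these would leave the model one-sided the other way if sessions are displaced.

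State whether acute MI is a separate cost item, so that an MI admission is counted once. State the perspective, horizon and unit of effect, since the perspective decides which items count.

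If this is not wanted, rename the outcome a hospital cost comparison and make no cost-effectiveness claim.

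Renaming costs only wording in two places. The full version adds a small costing effort and may give a less favourable cost figure. Neither changes the sample size, the visits or the primary analysis.
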